7.3. Treatment Assignment

Since this is an open-label study, all subjects that have cleared the inclusion/exclusion criteria will be administered ecopipam HCl at a target dose of 2 mg/kg/day.

7.4. Dose Adjustment Criteria

Doses will be adjusted based on the following weight bands to better achieve the 2 mg/kg/day target dose: ≥ 18 to ≤ 23 kg, > 23 to ≤ 34 kg, > 34 to ≤ 44 kg, > 44 to ≤ 68 kg, > 68 to ≤ 83 kg, > 83 kg. Dosing adjustments would be allowed down one dose level based on titration for safety reasons at the discretion of the Principal Investigator. See Section 10.5 for direction on administration of study drug.

7.5. Criteria for Subject Study Discontinuation

A subject may elect to discontinue from the study at any time for safety or personal reasons. All subjects who discontinue from the study should complete the early study discontinuation procedures.

Any subject with a new positive response on questions 4 and/or 5 of the C-SSRS will be immediately discontinued and evaluated for risk. Dosing may be restarted at the discretion of the Investigator following consultation with the Sponsor or its designee.

Subjects who discontinue early from the study will be discontinued for one of these primary reasons: AE(s), lost to follow-up, subject choice, inadequate therapeutic effect, and administrative/other. In addition to the primary reason, the subject may have indicated 1 or more of these reasons as secondary reasons for discontinuation. Study disposition information will be collected on the case report form (CRF).

 Table 2:
 Study Design and Schedule of Assessments

Assessment ⁴	Baseline* (Titration)					Tr	eatmo	End of Study / Early Termination	Follow Up Visit	Follow Up Phone Call					
Study Month	0	1	2	3	4	5	6	7	8	9	10	11	12	One and Two Weeks Post Last Dose	30 Days After Last Dose
Study Visit Number	1	2	3	4	5	6	7	8	9	10	11	12	13	14 & 15	
Visit Window		±3 days	±3 days	±3	±3	±3 days	±3 days	±3 days	±3 days	±3 days	±3 days	±3 days	±3 _{days}	±3 _{days}	±3days
Informed Consent	X														
Inclusion/ Exclusion	X														
Medical/Psychiatric/ Medication History	X														
Physical Examination	X	X		X			X			X			X	X	
Vital Signs ¹	X	X	X	X	X	X	X	X	X	X	X	X	X	X	
ECG	X	X		X			X			X			X		
Laboratory Tests (Hematology, Chemistry and Urinalysis) ²	X	X		X			X			X			X	X	
Urine Drug Screen	X	X		X			X			X			X		
Urine Pregnancy Test	X	X		X			X			X			X		
HbA1c		X		X			X			X			X		
YGTSS Score	X	X		X			X			X			X		
CGI-TS-I		X		X			X			X			X		

Confidential Page 34 of 76

Assessment ⁴	Baseline* (Titration)					Tr	eatm	End of Study / Early Termination	Follow Up Visit	Follow Up Phone Call					
Study Month	0	1	2	3	4	5	6	7	8	9	10	11	12	One and Two Weeks Post Last Dose	30 Days After Last Dose
Study Visit Number	1	2	3	4	5	6	7	8	9	10	11	12	13	14 & 15	
CGI-TS-S	X	X		X			X			X			X		
C&A-GTS-QOL	X	X		X			X			X			X		
Columbia Suicide Severity Rating Scale	X	X	X	X	X	X	X	X	X	X	X	X	X	X	
Abnormal Involuntary Movement Scale (AIMS)	X	X	X	X	X	X	X	X	X	X	X	X	X		
Barnes Akathisia Ratings Scale (BARS)	X	X	X	X	X	X	X	X	X	X	X	X	X		
Children's Depression Rating Scale-Revised (CDRS-R)	X	X	X	X	X	X	X	X	X	X	X	X	X		
Pediatric Anxiety Ratings Scale (PARS)	X	X	X	X	X	X	X	X	X	X	X	X	X		
Adverse Events	X	X	X	X	X	X	X	X	X	X	X	X	X	X	X
Concomitant Medications	X	X	X	X	X	X	X	X	X	X	X	X	X	X	
Dispense Study Drug	X	X	X	X	X	X	X	X	X	X	X	X	X^3		
Collect Unused Study Drug/Assess Drug Compliance		X	X	X	X	X	X	X	X	X	X	X	X	X	

Confidential

Abbreviations: BP = blood pressure, CGI = Clinician Global Impression, CGI-TS-I = CGI Tourette Syndrome of Improvement, CGI-TS-S = CGI Tourette Syndrome of Severity, ECG = electrocardiogram, HbA1c = Hemoglobin A1c

^{*} Baseline is to occur within 30 days of the EBS-101-CL-001 14 Day Follow Up Visit (or longer with the permission of the medical monitor). All Baseline measurements can be taken from the Day 14 Follow Up Visit of the EBS-101-CL-001 study if performed less than 7 days prior to the Baseline visit. In this case, the HbA1c and Urine Drug Screen from the Week 12/Completion Visit of the EBS-101-CL-001 study may be used.

¹ Vital signs will include heart rate, BP, orthostatic BP and heart rate (done supine and then 3 minutes after standing), height and weight.

² Subjects should be in a fasting state (8 hours) for laboratory tests.

³ Study drug dispensation for down titration.

⁴ Assessments for Study Visits may be completed in locations other than study clinic and/or safety and efficacy assessments required at these visits will be made available for remote administration due to restrictions as a consequence of the COVID-19 pandemic or other qualifying event.

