7. INVESTIGATIONAL PLAN

7.1. Overall Study Design

This is an international, multicenter, open-label, long-term extension study evaluating the safety of ecopipam tablets for the treatment of pediatric subjects (aged ≥6 to ≤18 years at Baseline) with TS. Subjects who completed the Phase 2b, randomized, double-blind, efficacy and safety study (EBS-101-CL-001) and who meet all the inclusion/exclusion criteria for this study will be eligible to participate in this study. All subjects will be titrated to a target dose of 2 mg/kg/day as participants rolling over from the Phase 2b double-blind efficacy and safety study will be tapered off of study medication to maintain the blind from that study. Subjects will complete study visits every month for 1 year. A Follow Up visits will be conducted 7 and 14 days after the last dose of study medication and a Follow Up phone call will be conducted 30 days after the last dose of study medication. Study Visits may be completed in locations other than clinic and/or safety and efficacy assessments required at these visits will be made available for remote administration due to restrictions as a consequence of the COVID-19 pandemic or other qualifying event.

Safety will be monitored throughout the study at every visit by repeated adverse event (AE) monitoring, vital signs, the Columbia-Suicide Severity Rating Scale (C-SSRS), the Abnormal Involuntary Movement Scale (AIMS), the Barnes Akathisia Rating Scale (BARS), the Pediatric Anxiety Rating Scale (PARS) and Children's Depression Rating Scale-Revised (CDRS-R). In addition to these assessments, at Baseline, Months 1, 3, 6, 9 and 12 safety will also be monitored by clinical and laboratory evaluations, and electrocardiogram (ECG) monitoring. In addition to the scales aforementioned, the YGTSS, CGI Tourette Syndrome of Severity (CGI-TS-S), and Gilles de la Tourette Syndrome—Quality of Life Scale for Children and Adolescents (C&A-GTS-QOL) will also be assessed at Baseline, Months 1, 3, 6, 9 and 12. The CGI-TS-I will be conducted at Months 1, 3, 6, 9, and 12. At the Follow Up visits, AE monitoring, the C-SSRS, clinical and laboratory evaluations and vital signs will be assessed. A Follow Up phone call will be conducted 30 days after the last dose of study medication to assess AEs.

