8.2. Subject Exclusion Criteria

- 1) Subjects with a clinical presentation and/or history consistent with another neurologic condition that may have had accompanying abnormal movements (e.g., Huntington's disease, Parkinson's disease, Wilson's disease, stroke, Restless Legs Syndrome).
- 2) History of schizophrenia, bipolar disorder, or other psychotic disorders.
- 3) Any unstable primary mood disorder (DSM-5 criteria) at time of Baseline.
- 4) Subjects who have unstable medical illness or clinically significant abnormalities on laboratory tests or ECG at Baseline as determined by the Principal Investigator.
- 5) Subjects who have moderate to severe renal insufficiency at Screening.
- 6) Subjects with a major depressive episode in the past 2 years.
- 7) Subjects with a history of attempted suicide.
- 8) A significant risk of committing suicide based on history, routine psychiatric status examination, Investigator's judgment, or who had an answer of "yes" on any question other than 1–3 (currently or within the past 30 days) on the baseline/screening version of the C-SSRS.
- 9) Subjects with a history of seizures (excluding febrile seizures that occurred <2 years prior to Baseline).
- 10) Subjects with a myocardial infarction within 6 months.

- 11) Female subjects who are currently pregnant or lactating or planning to become pregnant during the course of the study.
- 12) Subjects who have a need for medications which would have unfavorable interactions with ecopipam, e.g., dopamine antagonists or agonists [including bupropion], tetrabenazine, monoamine oxidase inhibitors, or St. John's Wort.
- 13) Subjects with current or recent (past 3 months) DSM-5 substance use disorder (with the exception of nicotine).
- 14) Subjects with positive urine drug screen for cocaine, amphetamine, methamphetamine, benzodiazepines, barbiturates, phencyclidine (PCP) or opiates at Baseline, except those receiving stable, prescribed treatment for ADHD. Subjects with urine positive only for benzodiazepines will be exclusionary unless medically prescribed.
- 15) Subjects with a lifetime history of bipolar disorder type I or II, dementia, schizophrenia, or any other psychotic disorder.
- 16) Inability to swallow tablets.
- 17) Subjects with a known hypersensitivity to ecopipam or any of its excipients.
- 18) Any subject who in the opinion of the investigator is not a suitable candidate for the study.

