10.5. Administration

Ecopipam HCl will be supplied as 12.5-, 37,5-, 50-, 75-, and 100-mg tablets. The target dose is 2 mg/kg via oral administration.

During the 4-week titration period, the following ecopipam HCl doses will be administered for each of the weight bands:

- Those who weigh ≥18-≤23 kg will titrate from 12.5 mg daily to 37.5 mg daily: 12.5 mg during Week 1, 25 mg (two 12.5-mg tablets) during Week 2, and 37.5 mg during Weeks 3 and 4.
- Those who weigh >23- \leq 34 kg will titrate from 12.5 mg daily to 50 mg daily: 12.5 mg during Week 1, 25 mg (two 12.5-mg tablets) during Week 2, 37.5 mg during Week 3, and 50 mg during Week 4.
- Those who weigh >34- \leq 44 kg will titrate from 12.5 mg daily to 75 mg daily: 12.5 mg during Week 1, 25 mg (two 12.5-mg tablets) during Week 2, 50 mg during Week 3, and 75 mg during Week 4.
- Those who weigh >44- \leq 68 kg will titrate from 25 mg daily to 100 mg daily: 25 mg (two 12.5-mg tablets) during Week 1, 50 mg during Week 2, 75 mg during Week 3, and 100 mg during Week 4.
- Those who weigh >68- \leq 83 kg will titrate from 25 mg daily to 150 mg daily: 25 mg (two 12.5-mg tablets) during Week 1, 50 mg during Week 2, 100 mg during Week 3, and 150 mg (two 75-mg tablets) during Week 4.
- Those who weigh >83 kg will titrate from 25 mg daily to 200 mg daily: 25 mg (two 12.5-mg tablets) during Week 1, 50 mg during Week 2, 100 mg during Week 3, and 200 mg (two 100-mg tablets) during Week 4.

During the treatment phase, the following ecopipam HCl doses will be administered for each of the weight bands:

- Those who weigh $\ge 18 \le 23$ kg will receive 37.5 mg daily.
- Those who weigh >23-\(\le 34\) kg will receive 50 mg daily.
- Those who weigh >34-\(\le 44\) kg will receive 75 mg daily.
- Those who weigh >44-\(\le 68\) kg will receive 100 mg daily.
- Those who weigh >68-\le 83 kg will receive 150 mg daily.
- Those who weigh >83 kg will receive 200 mg daily.

All doses will be administered PO once daily in the evening.

At the end of the open-label treatment phase, subjects will titrate off therapy and receive ecopipam HCl doses that will be reduced by 25 mg/day until off of drug; signs of symptoms of withdrawal will be monitored.

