6.2. Key Definitions

Treatment emergent adverse events (TEAEs) are defined as any adverse events that start or increase in intensity on or after the first dose of open-label treatment on Day 1.

Duration of exposure is defined as (Date of Last Dose – Date of First Dose) +1. If date of last dose is unknown, then the date of last clinical visit will be used to impute the date of last dose.

Baseline is defined as the last measurement taken before the first dose of open-label treatment on Day 1.

Change from baseline will be calculated for the post-baseline assessment as post-baseline value – baseline value.

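### Table 2's carry-over footnote lets the first dose rest on a C-SSRS up to 6 days old and on a still older urine drug screen; both could cheaply be done at Visit 1

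*Protocol*

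**What the plan says.** Table 2 (Protocol 7.5) marks the C-SSRS, the urine drug screen, the eligibility review and the dispensing of study drug at Visit 1. Footnote * relaxes this for subjects who roll over quickly: "All Baseline measurements can be taken from the Day 14 Follow Up Visit of the EBS-101-CL-001 study if performed less than 7 days prior". It adds that, in this case, "the HbA1c and Urine Drug Screen from the Week 12/Completion Visit of the EBS-101-CL-001 study may be used".

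Two exclusion criteria in Protocol 8.2 depend on these tests:

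- Criterion 8 excludes on a positive answer beyond question 3, "currently or within the past 30 days) on the baseline/screening version of the C-SSRS". It also excludes on significant suicide risk judged from history, psychiatric examination or the investigator's opinion.
- Criterion 14 excludes on a positive screen for any of a list of drugs ending "phencyclidine (PCP) or opiates at Baseline, except those receiving stable, prescribed treatment for ADHD".

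SAP 6.2 accepts whatever value came last: "Baseline is defined as the last measurement taken before the first dose of open-label treatment on Day 1". It sets no maximum age. Neither document asks for a repeat before dispensing when carry-over is used.

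**The concern.** For most Baseline data a value a few days old does no harm. The C-SSRS and the drug screen are different, because each decides whether a child may be dosed.

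Under carry-over, the days between the parent Day 14 visit and Visit 1 are covered by history, examination and judgment but not by the structured scale. A new positive answer beyond question 3 in that interval is found only if it is volunteered or noticed. The next scheduled C-SSRS is at Month 1.

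The check matters because of the drug's record. Protocol 5.2.2.1 reports that the Phase 3 obesity studies were discontinued for psychiatric events (31% on ecopipam, 15% on placebo), suicidal ideation among them. Protocol 5.3.1 reports suicidal ideation in pediatric subjects on ecopipam. Protocol 7.5 and 8.3 already make a new positive on question 4 or 5 a reason for immediate discontinuation, so the protocol itself treats this scale as decisive.

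The drug-screen consequence is narrower: a subject who became positive after the parent Week 12 visit could be dosed. Criterion 13 does not fill that gap, because it concerns a diagnosed substance use disorder and not a test result.

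**Working it through.** The plan gives no figure to reproduce; the check is a count of days.

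**Age of a carried-over C-SSRS at Visit 1**

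- Input: the under-7-day limit in footnote *.
- In whole days this is 0 to 6. At 0 days (both visits on the same day) there is no gap. At 1 to 6 days the form does not describe the subject's state at Visit 1.
- Against criterion 8's look-back, at most 6/30 = 20% of the days are not covered by the scale, even if the carried-over form had the 30-day look-back. This is calendar coverage, not a measure of risk.

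**Time to the next structured assessment**

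- Inputs: Table 2 schedules the next C-SSRS at Month 1, ±3 days. SAP 6.4 gives Month 1 a target of Day 29; that table was written for laboratory, vital-sign, ECG and examination data and serves here only for the monthly spacing. Assume the first dose is taken on the day of Visit 1 (Day 1).
- Without carry-over: 29 − 1 = 28 days, or 28 + 3 = 31 with the window.
- With carry-over: up to 28 + 6 = 34 days, or 34 + 3 = 37 with the window.
- Protocol 10.5 brings every weight band to its maintenance dose by Week 4, that is, by Day 22 (Week 3 in the lightest band). Month 1 falls on Day 26 at the earliest (29 − 3), so it follows titration to full dose.

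**Age of the drug screen at Visit 1**

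The footnote states no age. It is bounded only indirectly, because the screen is accepted only when the Day 14 visit was 0 to 6 days earlier. The interval from Week 12 to that visit is not in the documents, so it is assumed.

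- Protocol 7.1 says that "participants rolling over from the Phase 2b double-blind efficacy and safety study will be tapered off of study medication to maintain the blind", but gives no parent taper schedule. In this study subjects "receive ecopipam HCl doses that will be reduced by 25 mg/day until off of drug" (Protocol 10.5).
- Borrowing that step, reduced-dose days = ceil(dose/25) − 1. The lowest maintenance dose gives ceil(37.5/25) − 1 = 1; the highest gives ceil(200/25) − 1 = 7.
- Age = taper days + 14 + (0 to 6), taking Week 12 as the last full-dose day.
- With a taper: from 1 + 14 + 0 = 15 to 7 + 14 + 6 = 27 days.
- With no taper interval: from 14 + 0 = 14 to 14 + 6 = 20 days.
- Applying this study's ±3-day window to the Day 14 visit widens the combined 14 to 27 days to 11 to 30.

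Roughly 2 to 4 weeks is as precise as the assumption allows.

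**After the change**

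Both tests would be done at Visit 1, so their age at dispensing would be 0 days.

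**The case against.** The strongest reply is that no error has been shown. The footnote is an explicit roll-over rule with a stated cut-off, and preferring 0 days to at most 6 is a matter of judgment. Criterion 8's history, examination and judgment limbs cover the same days. Psychiatric history, adverse events and concomitant medication are reviewed at Visit 1, and criteria 3 and 18 give further grounds to exclude. A gap of up to 6 days before dosing is short beside the monthly interval accepted on drug. The first week's dose is only 12.5 or 25 mg. The cited suicidality events occurred on drug, and Protocol 5.2.2.1 reports no evidence of an effect on the C-SSRS in the earlier pediatric study. For the drug screen, the footnote says which result may serve, the screen is repeated at Month 1, and the documents give no harm data.

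Most of this stands and limits the size of the point. It does not supply the structured answer about the present that criterion 8 asks for.

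Two practical objections also stand. The change is a protocol amendment needing ethics approval (Protocol 16.1) across approximately 60 sites. SAP section 10 also lists updates made after database lock, so the change would come too late to alter eligibility checks in this study; it would serve a later roll-over study.

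A reader might infer three stronger things that the documents do not support:

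- **That the footnote contradicts or waives criterion 8.** It does neither. It says when a measurement may be taken, and the criterion still applies in full.
- **That the wrong C-SSRS form was used.** Criterion 8 still names the baseline/screening version, and the form used at the parent visit is not in the documents.
- **That risk is raised in the days before the first dose.** The cited events do not show this.

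**Conclusion.** The point holds as a cheap improvement of low to moderate priority. Where carry-over is used and the visits are on different days, the structured suicidality check is 1 to 6 days old at Visit 1 and is not scheduled again until after titration to full dose. The drug screen is a secondary matter. Its age of roughly 2 to 4 weeks depends wholly on the assumption that the parent taper and follow-up timing resemble this study's.

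This is an optional loosening of how criteria 8 and 14 are checked. It would be wrong to conclude that children are dosed with no suicide-risk check, since the clinical limbs of criterion 8 and criteria 3, 13 and 18 remain in force. Carry-over is a choice, the number of subjects using it is unknown, and no harm from it is documented.

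**What to change.** Amend footnote * to Table 2 in two steps, in order of priority:

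1. Take the C-SSRS out of the carry-over permission. Require it at Visit 1, in the version criterion 8 names, before study drug is dispensed.
2. Take the urine drug screen out of the sentence that allows the parent Week 12 result, leaving HbA1c there, and require the screen at Visit 1 before dispensing.

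Table 2 already marks both tests at Visit 1, and criteria 8 and 14 stay as written. No SAP change is needed: under SAP 6.2 the Visit 1 C-SSRS becomes the Baseline value.

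The burden falls only on carry-over subjects: about 5 minutes for the scale (Protocol 12.1) and one urine sample. The documents do not say whether the screen is read on site. If it goes to a laboratory, dispensing may have to wait for the result, as criterion 14 already implies for subjects who do not use carry-over. If that delay is unacceptable, the first step can be taken alone.

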8. SELECTION AND WITHDRAWAL OF SUBJECTS

8.1. Subject Inclusion Criteria

- 1) Subjects must have completed the EBS-101-CL-001 study through the Day 14 Follow Up Visit within the last 30 days (or with permission of the medical monitor) and must be who the Investigator feels would benefit from continued participation.
- 2) Adolescent females of childbearing potential who are sexually active must be using highly effective contraception (i.e., oral contraceptives, intrauterine device, intrauterine hormone-releasing system, bilateral tubal occlusion, vasectomized male partner) and agree to continue use of highly effective contraception for the duration of their participation in the study. They must also agree to use contraception for 30 days after their last dose of study drug.
- 3) Sexually active male subjects must use a highly effective method of contraception during the study and agree to continue the use of highly effective contraception for at least 30 days after the last dose of study drug.
- 4) Parents or legal guardians of subjects <18 years of age at Baseline must execute a written informed consent. Subjects ≥18 years of age must execute a written informed consent.
- 5) Subjects <18 years of age at Baseline must execute a written informed assent according to the requirements of the site's IRB/EC.

8.2. Subject Exclusion Criteria

- 1) Subjects with a clinical presentation and/or history consistent with another neurologic condition that may have had accompanying abnormal movements (e.g., Huntington's disease, Parkinson's disease, Wilson's disease, stroke, Restless Legs Syndrome).
- 2) History of schizophrenia, bipolar disorder, or other psychotic disorders.
- 3) Any unstable primary mood disorder (DSM-5 criteria) at time of Baseline.
- 4) Subjects who have unstable medical illness or clinically significant abnormalities on laboratory tests or ECG at Baseline as determined by the Principal Investigator.
- 5) Subjects who have moderate to severe renal insufficiency at Screening.
- 6) Subjects with a major depressive episode in the past 2 years.
- 7) Subjects with a history of attempted suicide.
- 8) A significant risk of committing suicide based on history, routine psychiatric status examination, Investigator's judgment, or who had an answer of "yes" on any question other than 1–3 (currently or within the past 30 days) on the baseline/screening version of the C-SSRS.
- 9) Subjects with a history of seizures (excluding febrile seizures that occurred <2 years prior to Baseline).
- 10) Subjects with a myocardial infarction within 6 months.

- 11) Female subjects who are currently pregnant or lactating or planning to become pregnant during the course of the study.
- 12) Subjects who have a need for medications which would have unfavorable interactions with ecopipam, e.g., dopamine antagonists or agonists [including bupropion], tetrabenazine, monoamine oxidase inhibitors, or St. John's Wort.
- 13) Subjects with current or recent (past 3 months) DSM-5 substance use disorder (with the exception of nicotine).
- 14) Subjects with positive urine drug screen for cocaine, amphetamine, methamphetamine, benzodiazepines, barbiturates, phencyclidine (PCP) or opiates at Baseline, except those receiving stable, prescribed treatment for ADHD. Subjects with urine positive only for benzodiazepines will be exclusionary unless medically prescribed.
- 15) Subjects with a lifetime history of bipolar disorder type I or II, dementia, schizophrenia, or any other psychotic disorder.
- 16) Inability to swallow tablets.
- 17) Subjects with a known hypersensitivity to ecopipam or any of its excipients.
- 18) Any subject who in the opinion of the investigator is not a suitable candidate for the study.

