6. STUDY OBJECTIVES AND PURPOSE

6.1. Primary Objective

The primary objective of this study is to evaluate the long-term safety and tolerability of ecopipam tablets in pediatric subjects (aged ≥ 6 to ≤ 18 years at Baseline) with TS that were previously enrolled in study EBS-101-CL-001 within the time period specified for this protocol.

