3.4.2. Exclusion Criteria

Subjects will not be eligible if they meet any of the criteria listed in section 8.2 of the protocol.

This document is confidential.

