3.5. Determination of Sample Size

This is a one-year safety and tolerability study as a follow up to the double-blind study (EBS-101-CL-001) and number of subjects enrolled in this is dependent on the number of subjects completing that study.

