Adverse Events of Special Interest (AESI) for ecopipam include Convulsions, Depression and Suicide/Self Injury, Drug Abuse, Dependence and Withdrawal, Dyslipedaemia, Hepatic Disorders, Hyperglycaemia/New Onset Diabetes Mellitus, NMS, and Psychosis and Psychotic Disorders.

AESI for Parkinsonism include Ataxia, Confusional state, Coordination abnormal, Somnolence, Disturbance in attention, Dyskinesia, Hyperkinesia, Gait disturbance, Memory impairment, Tremor, Vertigo, Agitation, Anxiety, Disturbance in attention, Dystonia, Bradykinesia, Musculoskeletal stiffness, Dysstasia, Gait disturbance, Posture abnormal, Balance disorder, Movement disorder, Movement disorder, Dyskinesia, Muscle rigidity, Coordination abnormal, Muscle contracture, Bradykinesia, Gait disturbance, Terminal insomnia, Nightmare, Poor quality sleep, Sleep disorder, Fatigue, Dizziness, Balance disorder, Restlessness, Amnesia, Confusional state, Dementia, Mental impairment, Speech disorder, Dysphonia, Vocal cord dysfunction, Parosmia, Anosmia, Urinary incontinence, Anxiety, Apathy, Joint stiffness, Reduced facial expression, Confusional state, Flat affect, Constipation, Depression, Dysphagia, Drooling, Fall, Fear of falling, Loss of visual contrast sensitivity, Muscle tightness, Dysgraphia, Dyskinesia, and Weight decreased.

AESI summary tables are listed below:

- AESI for ecopipam overall and by system organ class and preferred term
- AESI for Parkinsonism overall and by system organ class and preferred term.

In this summary, a patient is counted once at the system organ class and once at each preferred term within the system organ class.

- 14) Most common AEs ($\geq 5\%$) first onset experienced during treatment period will be summarized by month and preferred term.
- 15) Most common AEs ($\geq 5\%$) new incidence or ongoing, experienced during treatment period will be summarized by month and preferred term.

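### Exclusion 9 exempts only recent febrile seizures and bars all older ones, the reverse of the other look-back windows in Protocol 8.2

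*Protocol*

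**What the plan says.** Protocol 8.2, criterion 9, excludes "Subjects with a history of seizures (excluding febrile seizures that occurred <2 years prior to Baseline". The Synopsis carries the same words with the same inequality sign. Nothing else in the protocol defines or qualifies the exemption. The SAP adds no rule of its own; its section 3.4.2 says "Subjects will not be eligible if they meet any of the criteria listed in section 8.2 of the protocol".

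Other criteria in 8.2 also set a time limit on an event. Criterion 6 excludes "Subjects with a major depressive episode in the past 2 years" and criterion 10 "Subjects with a myocardial infarction within 6 months". Criterion 8 looks back 30 days on the C-SSRS, and criterion 13 looks back 3 months for substance use disorder.

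The population in Protocol 6.1 is "pediatric subjects (aged ≥ 6 to ≤ 18 years at Baseline". Entry is limited to subjects who completed EBS-101-CL-001 (Protocol 8.1, inclusion 1). Criterion 18 also lets the site turn away "Any subject who in the opinion of the investigator is not a suitable candidate for the study".

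**The concern.** Inside an exclusion criterion, a parenthesis beginning with the word excluding marks an exemption. Here the exemption is given to the recent event and withheld from the remote one. No rationale is offered, and no other time-limited criterion in 8.2 behaves this way, so the direction looks like a drafting slip rather than a choice.

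This is an operative eligibility rule. A site that follows it to the letter turns away a completer with a single febrile seizure in infancy. A site that reads through it to some presumed intent applies a different rule, and its decisions may be recorded as deviations. The pool cannot be topped up, because the "number of subjects enrolled in this is dependent on the number of subjects completing that study" (SAP 3.5). Seizure history also has some bearing on interpretation, since the SAP states that "Adverse Events of Special Interest (AESI) for ecopipam include Convulsions".

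**Working it through.** The plan gives no figure to reproduce here. The check is a reading of the rule, followed by subtraction.

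**Step 1. The rule as written (Protocol 8.2 and Synopsis, criterion 9).**

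| History | Result under criterion 9 |
|---|---|
| Non-febrile seizure, any time | Excluded |
| Febrile seizure 2 or more years before Baseline | Excluded |
| Febrile seizure less than 2 years before Baseline | Not excluded |

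**Step 2. Direction of the other windows (Protocol 8.2).**

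| Criterion | Window | Recent event | Remote event |
|---|---|---|---|
| 6, major depressive episode | 2 years | Excludes | Does not exclude |
| 8, C-SSRS answers | 30 days | Excludes | Not caught by the window |
| 10, myocardial infarction | 6 months | Excludes | Does not exclude |
| 13, substance use disorder | 3 months | Excludes | Does not exclude |
| 9, febrile seizure | 2 years | Does not exclude | Excludes |

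Only criterion 9 is reversed.

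**Step 3. Ages the exemption can reach.** A febrile seizure is exempt only if age at seizure > age at Baseline − 2.

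| Age at Baseline | Exempt only if the seizure came after age |
|---|---|
| 6 | 6 − 2 = 4 |
| 10 | 10 − 2 = 8 |
| 12 | 12 − 2 = 10 |
| 18 | 18 − 2 = 16 |

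The lowest threshold is 4, so a febrile seizure at or before the fourth birthday is never exempt for any eligible subject. SAP 3.1 ties the age range to the Baseline of the parent study instead. That does not change the result, because a subject aged 6 or more then is at least 6 at this Baseline.

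Two cases show the effect. A 10-year-old with one febrile seizure at age 2 (10 − 2 = 8 years earlier) is barred. A 6-year-old with one at age 5 (6 − 5 = 1 year earlier) is not barred by criterion 9.

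**Step 4. Losing the exemption by elapsed time.** The schedule footnote and inclusion 1 give three intervals: parent study to Week 12 (84 days), the Day 14 Follow Up Visit (14 days), and up to 30 days to this Baseline. I assume that Week 12 counts from parent-study entry and add nothing for parent screening or taper, whose lengths are not given.

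- Shortest gap: 84 + 14 = 98 days; 98 / 30.4 = 3.2 months.
- Longest gap without the medical monitor's permission: 84 + 14 + 30 = 128 days; 128 / 30.4 = 4.2 months.

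Take a febrile seizure 20 months before parent-study entry. At this Baseline it is 20 + 3.2 = 23.2 months old (exempt) or 20 + 4.2 = 24.2 months old (excluded), depending only on when the visit is booked. At the longest gap, any febrile seizure from 24 − 4.2 = 19.8 months to just under 24 months before parent-study entry crosses the line. Screening, taper or a permitted extension would widen that band.

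**The case against.** The best defence is that the practical effect may be very small. Every candidate has already passed the entry criteria of EBS-101-CL-001, and its seizure criterion is not in these documents. If it carries the same wording, children with older febrile seizures never entered the parent study. Criterion 9 here would then newly remove only those who cross the 2-year line in the gap shown in Step 4. Criterion 5 refers to Screening although this study's schedule has no screening visit, which hints that the list was carried over from another protocol but does not prove it. This objection stands, and it limits what can be said about size.

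One could also read the parenthesis as barring recent febrile seizures as well. That fails on the text: a history of seizures already covers them, so the parenthesis would do nothing. If the wording is nonetheless thought ambiguous, sites could apply opposite rules, which is itself a reason to fix it. A misprint in one copy is not the explanation either, since both copies agree.

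A reader might go further in three ways that the documents do not support.

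- **That the rule admits the children most likely to confound the convulsions category.** No passage shows that a recent febrile seizure raises that count. Suppose, as an assumption from outside the documents, that febrile seizures are largely over by about age 5. The exemption then reaches only subjects younger than about 7 (5 + 2), so the main effect is to exclude.
- **That such children are admitted.** They are only not barred by criterion 9. Criterion 4 (unstable medical illness), criterion 18 and the investigator's judgement of benefit in inclusion 1 still apply.
- **That a head count follows from a background rate times a roll-over total.** The documents give neither figure, and the product would ignore the filter already applied by the parent study.

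**Conclusion.** The point holds as a drafting defect in an operative criterion. As written in both places, criterion 9 exempts recent febrile seizures, bars older ones, and runs against criteria 6, 8, 10 and 13. For the stated age range, the exemption can never reach a febrile seizure at or before the fourth birthday, and it can lapse through scheduling alone. These conclusions need only the text and the age limits; the months in Step 4 also rest on the stated timing assumption.

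The number of subjects affected cannot be derived. It could be near zero if the parent criterion is worded the same way and larger if it is not. The defect can affect who enters the Safety Set, but it changes no endpoint, analysis-set definition or calculation. Confidence is high on the literal reading and low on the sponsor's intent and on the impact. The documents do not show which rule was meant, and the clinical threshold is for the sponsor to set.

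**What to change.** The sponsor should compare criterion 9 in Protocol 8.2 and the Synopsis with the parent protocol and with the direction of the other look-back windows. It should then reword both copies so that two things are explicit: which side of the 2-year limit is exempt, and whether the limit is measured as time before Baseline or as age at the seizure.

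Subjects screened under the current wording should be checked against planned SAP Listings 16.2.1.2 (Baseline Failure), 16.2.3.2 (Inclusion/Exclusion Criteria) and 16.2.4.2 (Medical History), with a statement of how sites applied the criterion. The first two listings are assigned to the Enrolled Set, which SAP 5.1 limits to subjects who met the criteria and enrolled, and the third to the Safety Set. A subject who was turned away may therefore appear in none of them, so the check should extend to the full database and site screening records.

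SAP section 10 records changes made after database lock, so rewording may no longer alter who was enrolled. It would still settle how existing decisions are classified and prevent reuse of the text. The cost is a one-line correction in two places and a check of existing records, with no new procedure or data collection.
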